8.3.4 Analysis related to secondary objectives

A detailed description of the secondary objectives and endpoints are found in section 5.2 of the protocol. The secondary endpoints will be based on both the FAS and the PP set.

HEAD-US scores (hypertrophic synovium, cartilage, bone) and HJHS scores (Sum of joint totals, Global Gait Score, HJHS total score) will be presented using descriptive statistics at each visit. In addition, the change from baseline to each post-baseline visit will also be presented with descriptive statistics and the estimated average change from baseline together with 95% CI.

The number and proportion of patients with target joints as well as the total number of target joints will be analyzed by summary statistics as well as frequency tables for each visit. Target joint locations will be given for each visit in frequency tables.

The ABR for treated bleeds and ABR for all (treated and untreated bleeds) will be derived for the period between baseline and month 6 visit, for the period between month 6 and month 12 visit, for the period between month 12 and month 18, and as well as for the entire 18-month study period. The ABR will also be presented for the retrospective 6 month period. ABR will be presented using summary statistics for all periods and also be presented by type (spontaneous/traumatic/unknown) and location (joint/muscle/unknown). The number and

Sobi

Eftrenonacog alfa/Alprolix® - Efmorocog alfa/Elocta®

Clinical Study No: Sobi.HAEM89-007

percentage of patients who had at least one bleeding episode (overall, circumstance, locations and target joint) over the 18-month prospective period will also be presented as well as the corresponding total number of episodes. The number and proportion of patients with 0 joint bleeds will be presented, as well as the number and proportions with 1, 2 etc. joint bleeds. To justify an estimation of the ABR and to reduce potential misclassification, a patient had to be documented for at least 3 months.

PROMIS and IPAQ-SF scores will be presented at baseline and 18 months graphically and in tabular form with descriptive statistics (mean IPAQ-SF score measured as MET-minutes/week) and change.

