6.3.3 Withdrawal of patients from study

6.3.3.1 Withdrawal from study

Whenever possible and irrespective of the reason for withdrawal, the patient should be examined as soon as possible. All relevant assessments should be completed, preferably according to the schedule of events (see section 6.5.1.1). The Case report form (CRF) should be completed as far as possible. Date and reason for the study withdrawal should be clearly described in the CRF.

A patient should be withdrawn from the study for any one of the following reasons:

- The patient develops factor VIII or FIX inhibitory antibodies (inhibitor titre ≥ 0.60 BU/mL)
- The patient or his legally authorized representative(s) withdraws consent
- The patient enrolls into an interventional clinical study in which an investigational treatment or approved therapy for investigational use is administered
- The patient enrolls into a low-interventional clinical study where the assessments performed are of such nature that the patient cannot be considered treated per usual routine practice
- The patient discontinues prophylactic treatment with rFVIIIFc or rFIXFc
- The patient is no longer willing to undergo the mandatory US examination

If any Adverse Event (AE) is associated with the withdrawal this should be recorded in the CRF.

If the patient withdraws consent for disclosure of future information (data, samples), the sponsor may retain and continue to use any data collected before such a withdrawal of consent.

Patients will not be withdrawn if they miss a study visit.

If a patient withdraws from the study and more than 3 months since the last study visit have passed, all assessments should be performed to the extent possible. If a patient withdraws from the study less than 3 months since the last visit, PRO collection and HJHS assessment should be performed to the extent possible.

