6.3.4 Replacement of withdrawn patients

Withdrawn patients will not be replaced.

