8.2 Definition of study populations

Full analysis set (FAS): All patients enrolled in the study.

Per protocol (PP) analysis set: All patients enrolled in the study who completed the study without any major protocol violations.

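### Section 8.3.4 makes no allowance for unequal follow-up in the FAS tables of patients with 0, 1, 2 or more joint bleeds, so early withdrawals would raise the bleed-free share

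*Combined protocol and SAP*

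**What the plan says.** Section 8.3.4 gives the number and percentage of patients with at least one bleeding episode "over the 18-month prospective period will also be presented as well as the corresponding total number of episodes". The next sentence adds: "The number and proportion of patients with 0 joint bleeds will be presented", with the same for 1, 2 and so on. That second sentence names no period. The 18 months is carried over from the sentence before it.

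On populations, the same section says "The secondary endpoints will be based on both the FAS and the PP set". Section 8.2 defines the first as "Full analysis set (FAS): All patients enrolled in the study" and the per-protocol set as "All patients enrolled in the study who completed the study without any major protocol violations".

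The only follow-up requirement in 8.3.4 comes straight after the joint-bleed sentence: "To justify an estimation of the ABR and to reduce potential misclassification, a patient had to be documented for at least 3 months".

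Section 6.3.3.1 lists the reasons for taking a patient out of the study. They include inhibitor development, refusal of further ultrasound, entry into certain other studies, and "The patient discontinues prophylactic treatment with rFVIIIFc or rFIXFc". Section 6.3.4 adds: "Withdrawn patients will not be replaced". Section 8.3.8 leaves missing-data methods to the SAP, and the supplied text contains no separate SAP section that deals with this table.

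**The concern.** A percentage with zero events is an 18-month percentage only if everyone in the denominator was watched for 18 months. The annualized bleeding rates are scaled by observation time, and these percentages are not. A patient who leaves at month 4 with no joint bleed has a recorded count of zero and looks the same as a patient who went 18 months without one.

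Unobserved time can hide bleeds but cannot add them. Early withdrawal therefore raises the FAS share with no bleed, lowers the share with at least one, and shifts the 0/1/2 distribution towards low counts. A larger sample does not reduce this, and with no control arm nothing offsets it. A general missing-data rule may not catch it either, because withdrawal leaves a count of zero and not a visibly missing value. At stake is a figure that serves the secondary objective of describing bleeding over 18 months.

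**Working it through.** **Plan's own figures.** The plan states no figure for this table. Its only design calculation is the precision of the HEAD-US change: 1.96 × 13/√250 = 1.61, which matches Table 3 but has no bearing here.

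**Inputs.** From the documents: T = 1.5 years, N = 250, FAS = all enrolled. Assumed, because the documents give none of them: joint-bleed rate r = 0.25 to 2 per year; Poisson counts, or negative binomial with dispersion k = 2; a fraction d lost, with withdrawal spread evenly over 18 months and unrelated to bleeding.

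**Formulas.**
- Probability of no joint bleed by time t: P0(t) = exp(−rt) (Poisson) or (1 + krt)^(−1/k) (negative binomial).
- Target: P0(1.5).
- Crude FAS proportion: (1 − d) × P0(1.5) + d × M, where M is the mean of P0 over withdrawal times 0 to 1.5.
- With the 3-month rule, leavers before 0.25 years drop out of numerator and denominator, so a fraction f = 1.25/1.5 = 0.833 of leavers remains, with mean M3.

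**Worked example: Poisson, r = 0.5, d = 10%.**
- Target: exp(−0.75) = 47.2%.
- M = (1 − 0.4724)/0.75 = 0.7035.
- Crude: 0.9 × 0.4724 + 0.1 × 0.7035 = 49.5%, an excess of 2.3 points.
- M3 = (exp(−0.125) − exp(−0.75))/(0.5 × 1.25) = 0.6562.
- Crude with the 3-month rule: (0.9 × 0.4724 + 0.1 × 0.833 × 0.6562)/(0.9 + 0.0833) = 48.8%, an excess of 1.6 points.

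**Range over both models and r = 0.25, 0.5, 1 and 2 (excess in percentage points).**

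| Loss by 18 months | No minimum follow-up | 3-month minimum |
|---|---|---|
| 5% | 0.5 to 1.5 | 0.3 to 0.9 |
| 10% | 1.1 to 2.9 | 0.7 to 1.9 |
| 20% | 2.1 to 5.9 | 1.4 to 3.8 |
| 30% | 3.2 to 8.8 | 2.2 to 5.8 |

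**Kaplan-Meier check.** Take gamma-distributed rates with mean 1 per year and shape 1, so that P0(t) = 1/(1 + t), and 20% exponential loss. The target is 1/2.5 = 40.0%. The crude figure is 0.8 × 40.0% plus 12.4% from early leavers, or 44.4%. In simulation Kaplan-Meier returns about 40%. If patients above the median bleed rate withdraw three times as fast, the crude figure is about 45% and Kaplan-Meier about 41%.

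**Opposing effect.** The month-18 window runs from −28 to +56 days (6.5.1.1, 6.5.1.5), and the EOS date is the date of the last assessment. With P0(t) = 1/(1 + t), 14 extra days (the window midpoint) give 1/2.538 = 39.4%, or −0.6 points. The full 56 days give 1/2.653 = 37.7%, or −2.3 points. A visit 28 days early gives 1/2.423 = 41.3%, or +1.3 points.

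**Scale.** The 95% CI half width for a proportion near 50% with n = 250 is 1.96 × √(0.25/250) = 6.2 points.

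**The case against.** The strongest reply is that the plan is silent here and not wrong. It nowhere states that early leavers are classed as bleed-free, and the SAP promised in 8.3.1 and 8.3.8 may supply the rule. That stands as to intent: the defect is what follows if the text is applied as it reads.

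A reader might infer that a headline result is overstated. The documents do not support that. The primary endpoint is HEAD-US change, the bleeding endpoints listed in 5.2.1 are all annualized rates, the 0-joint-bleed share is not among them, and no hypothesis testing is planned.

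The per-protocol version keeps completers only, so early withdrawals cannot enter it, and 8.3.2 reports withdrawals with reasons. This also stands. It does not repair the FAS figure, and completers are a selected group.

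The 3-month sentence follows the joint-bleed sentence directly and mentions misclassification, so it may be meant to cover the count categories. The text is ambiguous. On that reading a month-2 leaver is excluded, but a patient seen for 3 months still counts as bleed-free over 18.

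It would also be tempting to say that the crude share can err only upward. That is true of early withdrawal, but not of the whole table, because late EOS visits lower the bleed-free share.

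Finally, at 10% loss the bias is smaller than the sampling error. That limits its importance, but the interval would still be centred on the wrong value.

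**Conclusion.** The point holds as a modest weakness in a supporting table. For the FAS, the proportions with at least one bleed and with 0, 1, 2 etc. joint bleeds are crude, with no allowance for unequal follow-up that the withdrawal rules make foreseeable. As 18-month figures, they are biased by early withdrawal towards fewer bleeds.

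The excess in the 0-joint-bleed share is about 1 to 3 percentage points at 10% loss and 2 to 6 at 20%. If the 3-month rule applies, it is about 0.7 to 1.9 and 1.4 to 3.8. These ranges rest on assumed bleed rates, dispersion and loss, with withdrawal even over time and independent of bleeding. They leave out the EOS window, which can offset part of the excess. The documents fix neither the actual size nor the net direction of the whole table, so they do not support a claim of demonstrated overstatement.

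**What to change.** In 8.3.4 or the SAP:

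- For the FAS, estimate the proportion free of joint bleeds, and the proportion free of any bleed, at a fixed 18-month time point by Kaplan-Meier on time to first bleed from baseline. Give a 95% CI and censor at withdrawal or last bleed documentation. The fixed time point also removes the effect of the EOS window.
- State how bleeds without a date are handled. Section 6.5.8 collects the date of each bleed, but footnote 3 of the schedule of events makes it subject to availability.
- Name the period for the 0/1/2 tables and say whether the 3-month rule applies to them.
- Keep those tables as observed counts, labelled as such, with follow-up time shown. Alternatively, limit them to patients with complete 18-month bleed documentation and give the number excluded.

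The cost is a few lines of text and one extra table, with no new data collection. The reported bleed-free share will probably be slightly less favourable. Kaplan-Meier stays slightly high if patients who bleed more also withdraw more (about 1 point in the three-fold example), and the report should say so.

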6.3.1 Inclusion criteria

A patient must fulfill the following criteria in order to be included in the study:

1. Age \geq 6 years
2. Diagnosis of haemophilia A or B
3. Having at least 6 months documented pre-study treatment data regarding treatment prescriptions and bleeding episodes prior to the baseline visit
4. Previous treatment for haemophilia A or B with any marketed recombinant and/or plasma-derived FVIII or FIX concentrate for at least 6 months
5. Start of prophylactic treatment with rFVIIIFc or rFIXFc prior to study enrolment or latest at the baseline visit, in accordance with local regulations
6. Signed and dated informed consent provided by the patient, or the patient's legally authorized representative for patients under the legal age. Assent should be obtained from paediatric patients in accordance with local regulations

6.3.1.1 florio HAEMO sub-study

To be eligible for the florio HAEMO sub-study a patient should have used florio HAEMO (a CE marked medical device used in routine clinical practice) for at least 3 months and must agree to have data collected from the florio HAEMO app by providing a separate informed consent or assent.

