8.3 Overall statistical and analytical plan

8.3.1 General statistical issues

A detailed Statistical Analysis Plan (SAP) describing further details of the statistical analyses to be used will be prepared prior to first patient in.

All continuous variables will be summarized with descriptive statistics including number of observations, mean, standard deviation, median, quartiles, minimum and maximum values. Categorical variables will be summarized in frequency tables including number of observed responses in each category as well as percentages. Number of missing observations will also be displayed. No formal statistical hypothesis testing is planned.

Baseline is defined as the measurements taken on Visit 1.

Historical data (6-months before enrolment) will be tabulated by type of haemophilia, total and listed.

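### The 3-month rule for ABR departs from the all-enrolled analysis set and understates the mean ABR if early leavers bleed more

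*Combined protocol and SAP*

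**What the plan says.** Section 8.3.4 of the protocol states: "The secondary endpoints will be based on both the FAS and the PP set". Section 8.2 defines the FAS as all enrolled patients, and the PP set as those who completed without major violations.

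ABR is derived for months 0–6, 6–12 and 12–18, "as well as for the entire 18-month study period", and also backwards: "The ABR will also be presented for the retrospective 6 month period". The method is descriptive: "ABR will be presented using summary statistics for all periods". Section 8.3.1 says what that means: "All continuous variables will be summarized with descriptive statistics including number of observations, mean, standard deviation, median, quartiles, minimum and maximum values". The condition for having an ABR at all is: "To justify an estimation of the ABR and to reduce potential misclassification, a patient had to be documented for at least 3 months".

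The section gives no ABR formula and no interval for ABR, although it plans 95% CIs for the HEAD-US item and HJHS changes. It does not say to which period the 3 months apply. It plans no ABR analysis without the rule and no account of the patients the rule removes.

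Three other places matter:

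- Section 6.3.1 requires of every patient: "Having at least 6 months documented pre-study treatment data regarding treatment prescriptions and bleeding episodes prior to the baseline visit".
- Section 6.3.3.1 withdraws patients who stop rFVIIIFc or rFIXFc prophylaxis or who develop an inhibitor. Section 6.3.4 does not replace them.
- Section 8.3.8 leaves missing data to the SAP.

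**The concern.** The rule selects patients on how long they stayed, and some reasons for leaving may be tied to how well bleeding is controlled. Inclusion criterion 5 lets patients start the product as late as the baseline visit. For those patients the first 3 months in the study are also the first 3 months on the product. If patients who leave in that window bleed more than the rest, the reported mean ABR describes those who stayed and is lower than the mean for all enrolled patients.

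The primary analysis takes another line. Section 8.3.3 keeps patients who discontinue, with the data collected up to that point. The reason given for the ABR rule, avoiding misclassification, does not deal with selection.

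The study has no control group, so readers will tend to set the prospective ABR beside the retrospective one. The rule can shrink only the prospective side of that contrast.

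**Working it through.** **The plan's own figure.** The plan states no ABR, ABR precision or dropout rate. Its sample-size figure (section 8.1) is for total HEAD-US score: 1.96 × 13/√250 = 1.61, as stated. It does not bear on ABR.

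**Whom the rule removes, by reading.**

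- 3 months of prospective follow-up: patients who leave before month 3 have no prospective ABR.
- 3 months within each period: the selection recurs. A patient who leaves at month 8 has 2 months in the 6–12 window and loses that ABR.
- 3 months of any documentation: nobody is removed, because everyone has at least 6 months of pre-study data.

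For the retrospective period nobody is removed under any reading. In the PP set the rule has no practical effect on the 18-month ABR, because that set holds completers only.

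**Effect of the exclusion alone.** Let a share d leave before 3 months with RR times the others' rate λ. The mean over all enrolled patients is λ[1 + d(RR − 1)]. The mean after the exclusion is λ. The relative bias is 1/[1 + d(RR − 1)] − 1. Both d and RR are assumptions.

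| d (of 250 patients) | RR 1 | RR 2 | RR 3 |
|---|---|---|---|
| 1% (2.5) | 0 | −1.0% | −2.0% |
| 2% (5) | 0 | −2.0% | −3.8% |
| 5% (12.5) | 0 | −4.8% | −9.1% |
| 10% (25) | 0 | −9.1% | −16.7% |

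**Direction of equal weighting.** Summary statistics of individual ABRs imply one patient, one weight. Assume 2% leave before 3 months, 10% leave between 3 and 18 months (0.875 years on average), 88% stay 1.5 years, leavers have RR 3 and stayers have rate 1.

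- Mean over all enrolled: 0.12 × 3 + 0.88 = 1.240.
- Planned mean, at least 3 months: (0.10 × 3 + 0.88)/0.98 = 1.204, or −2.9%.
- Pooled rate in the same patients: (0.10 × 3 × 0.875 + 0.88 × 1.5)/(0.10 × 0.875 + 0.88 × 1.5) = 1.5825/1.4075 = 1.124.

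Equal weighting gives the short-stay, high-bleeding patients more weight than exposure weighting does, so it raises the mean.

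**Simulation of the alternatives.** Assumed: 250 patients, base rate 2 per year, gamma-Poisson counts with dispersion 1.5, leaving times uniform within each window, 600 studies per case. The columns show average estimates, with bias against the true all-enrolled mean. The negative binomial (NB) model uses all patients and a log-time offset.

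| Leave <3 mo / 3–18 mo / RR | Truth | Planned mean | Unrestricted mean | NB model | SD of ABRs, with → without rule |
|---|---|---|---|---|---|
| 2% / 10% / 1 | 2.000 | 2.000 | 1.999 | 1.998 | 2.715 → 2.792 |
| 2% / 0 / 3 | 2.081 | 1.991 (−4.3%) | 2.072 (−0.4%) | 2.016 (−3.1%) | 2.671 → 3.063 |
| 5% / 0 / 3 | 2.200 | 2.012 (−8.5%) | 2.204 (+0.2%) | 2.079 (−5.5%) | 2.705 → 3.562 |
| 2% / 10% / 3 | 2.491 | 2.412 (−3.2%) | 2.483 (−0.3%) | 2.391 (−4.0%) | 3.739 → 4.021 |
| 5% / 10% / 3 | 2.603 | 2.425 (−6.8%) | 2.610 (+0.3%) | 2.455 (−5.7%) | 3.775 → 4.419 |
| 5% / 15% / 2 | 2.398 | 2.296 (−4.3%) | 2.376 (−0.9%) | 2.291 (−4.5%) | 3.289 → 3.666 |

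The unrestricted mean is nearly unbiased but noisier: the SD rises by 3% (2.792/2.715) to 32% (3.562/2.705). The model helps when the bias comes mainly from leavers before 3 months. It is slightly worse than the planned mean in two of the three cases where later leavers also bleed more.

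**The case against.** The case for leaving the plan alone is fair in several respects. ABR is a descriptive secondary endpoint in a single-arm study without hypothesis tests. The rule has a stated purpose, and the simulated SDs show that it does reduce noise. Medians and quartiles are reported too, and the exclusion does not pull the median down (1.193 with the rule and 1.179 without, in the 2% / 10% / RR 3 case). Early leavers are not hidden. Section 8.3.2 lists withdrawals with reasons, inhibitor development is an event of special interest, and the numbers of patients with bleeds and of episodes in section 8.3.4 carry no stated 3-month limit. Patients need 6 months of prior factor treatment and no current inhibitor, so a high-bleeding group of early leavers is possible but not shown. The detailed SAP that section 8.3.1 promises may settle the details.

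All of this limits the size and priority of the point. It does not remove it: patient counts and episode totals are not rates, and no planned ABR covers all enrolled patients.

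Three stronger readings are tempting, and none is supported:

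- A reader might infer that giving short and long follow-up equal weight also favours the product. When leavers bleed more, the direction is the reverse (1.204 against 1.124). The cost of equal weighting is noise. Equal weighting is itself an inference, since no formula is given.
- A reader might infer that the ABR is understated as a fact. That needs early leavers who bleed more, and the documents give neither their number nor their rate.
- A reader might infer that a negative binomial model should replace the planned summary. It does not reliably reduce the bias and can slightly increase it.

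**Conclusion.** The point holds as a minor one. On the natural reading, the 3-month rule contradicts the all-enrolled FAS for prospective ABR. It lowers the mean by about 1% to 9% if 1% to 5% of patients leave before 3 months with 2 to 3 times the others' rate, and by nothing if their rate is the same. The range rests on assumed inputs.

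The uneven contrast with the retrospective 6 months follows from the text once any patient leaves before 3 months: all patients qualify there, and only those who stay qualify afterwards. No test and no primary conclusion is affected. What is at stake is the absolute mean ABR and that informal contrast.

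**What to change.** In section 8.3.4 and the SAP:

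1. Give the ABR formula (bleeds divided by documented years) and state whether the 3 months apply to each period or to prospective follow-up as a whole.
2. Keep the planned summary of ABRs in patients with at least 3 months.
3. Add an ABR analysis in all FAS patients with any prospective follow-up: the unrestricted mean of individual ABRs, and a negative binomial model of bleed count with log(follow-up time) as offset, each with a 95% CI. Say in the text that neither the rule nor the model deals fully with informative withdrawal.
4. Report the number of patients the rule removes, with their bleeds, patient-time and reasons for leaving.
5. Show the retrospective ABR also for the patients who have a prospective ABR, so that the contrast can be read on the same people.

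The cost is one standard model, a few table rows and a noisier unrestricted mean, which very short follow-up can dominate. Bleeds must have been recorded up to withdrawal. For withdrawal less than 3 months after the last visit, section 6.3.3.1 names only PROs and HJHS, beside a general instruction to complete relevant assessments. The CRF instructions should therefore ask for bleeds and the last documented date.
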